Concerning the online questionnaires: the package 1 is constituted by the SSQ6, the MAIA-2 and the STAI Y-B. The package 2 is constituted by the Brief-Cope, the BFI-N and the CTQ. The package 3 is constituted by the DHS. The package 4 is constituted by the BVAQ-B and the LE

II : Statistical analysis plan

Independent variables

Analysis A:

The participants will be separated into two inter-subject groups:

- An experimental group performing BFB technique in the intervention phase (T2-T3)
- A control group no performing an exercise in the intervention phase (T2-T3)

The participants won't be informed of the condition to which they belong.

Independent variables

- Measurement time (T1 / T2 / T3) intra-subject
- Group (experimental group / control group) inter-subject

Analysis B:

The participants will be separated into two inter-subject groups performing by a cluster analysis (HF or RMSSD) in the first session (T1):

- A dysfunctional neurovegetative profile (low vagal tone + low vagal flexibility) group
- A functional neurovegetative profile (high vagal tone + high vagal flexibility) group

The participants won't be informed about their neurovegetative profile. We will include all the participants.

Independent variable

- Neurovegetative profile (dysfunctional profile / functional profile) inter-subject

Analysis C:

The participants will be separated into two inter-subject groups performing by a cluster analysis (HF or RMSSD) in the first session (T1):

- A dysfunctional neurovegetative profile (low vagal tone + low vagal flexibility) group
- A functional neurovegetative profile (high vagal tone + high vagal flexibility) group

The participants won't be informed about their neurovegetative profile. We will include only the experimental group performing the BFB technique.

Independent variables

- Neurovegetative profile (dysfunctional profile / functional profile) inter-subject
- Measurement time (T2 / T3) intra-subject

Dependent variables

Physiological variables:

ECG –HRV:

- HF (0.15-0.40 Hz – high frequency) frequency-domain parameter
- LF (0.04-0.15 Hz – low frequency) frequency-domain parameter
- LF-0.1 Hertz (0.075-0.108Hz - spectral power of the low-frequency 0.1Hz band) frequency-domain parameter
- LF/HF (ratio of LF to HF power) frequency-domain parameter
- Total power (total power of the 0-0.40 Hertz band) frequency-domain parameter
- RMSSD (root mean square of successive RR interval differences) temporal-domain parameter

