- SDNN (standard deviation of all NN intervals) temporal-domain parameter
- EDR (ECG-derived-respiration)

GSR (tonic GSR / phasic GSR):

- SCR frequency: number of the spontaneous galvanic skin responses by periods
- SCR amplitude: amplitude of the spontaneous galvanic skin responses by periods
- Integrated skin conductance responses [ISCR]: area of the galvanic skin responses identified on the signal

PPG:

- Pulsatility index variation (PI): Transit time flow

Breathing belt:

- Breathing rate by cycles per minute

EGG:

- Dominant power
- Total power [0-0.15 Hertz]
- Slow-waves frequency per minute

EEG:

- Spontaneous brain rhythms: spectral power of the 0-30 Hertz band

Physiological adaptation to the aversive situation (emotional reactivity task):

HRV, GSR and PPG differences will be calculated to measure the physiological changes causing by the task compared to the resting and the recovery periods. The differences will be calculated as follows:

- Physiological reactivity during the task compared to the resting period (Δ = reactivity HRV – resting HRV / Δ = reactivity GSR – resting GSR / Δ = reactivity PPG – resting PPG)
- Physiological recovery following the task (Δ = recovery HRV – reactivity HRV / Δ = recovery GSR – reactivity GSR / Δ = recovery PPG – reactivity PPG)

- Physiological recovery following the task compared to the resting period (Δ = recovery HRV – resting HRV / Δ = recovery GSR – resting GSR / Δ = recovery PPG – resting PPG)

Psychological variables:

- Alexithymia score (BVAQ-B)
- Neuroticism score (BFI-N)
- Trait anxiety score (STAI Y-B)
- Style of coping (Brief Cope)
- Positive affectivity score (PANAS)
- State anxiety score (STAI Y-A)
- Depressive symptoms score (CES-D)
- Perceived-stress level (PSS)
- Coping flexibility + metacoping scores (CFS + VAS)
- Acceptance score (ICQ-18)
- Social support score (SSQ6)
- Interceptive sensitivity score (MAIA-2)
- Life satisfaction score (SWLS)
- Negative impact scores (LES)
- Frequency, severity and intensity scores (DHS)
- Abuse scores (CTQ)

Statistical analyses

All statistical analyses will be performed using IBM SPSS Statistics®, R software® and JASP®. The alpha value for statistical significance will set at $p<0.05$.

Analyses of the scores collected will be done in several stages:

- Highlighting outlier participants to exclude from our statistical analysis.
- All the conditions for application of statistical tests will be verified.

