- In the case of a failure to respect the conditions for parametric test application, we would make a data transformation to jointly improve normality and homogeneity residues. If the normality is failed and the homogeneity is respected, we would execute non-parametric tests.
- Analysis will be done on the subjects included. Analysis concerning the reactivity period (during the task) will be performed on the all blocs excepted the bloc 1².
- Main and secondary judgment criterions analysis will be performed by parametric tests or by non-parametric tests depending on the conditions for application:

• *Analyse A:*

- An ANOVA to repeated measurement with an intra factor (measurement time: T1 / T2 / T3) and an inter factor (group: experimental / control) on the physiological and psychological data collected.
- Student's test for independent samples will be performed on the psychological scores collected in the second session (T2) to account for the initial level of psychological states between the 2 groups.

² The bloc 1 will not be included in the final statistical analysis because is considered as a training bloc. This choice in accordance to the potential biases related to the increase of the sympathetic activity at the beginning of the task caused by a simple moving to action following the resting period.

- Contrasts will then be made by group on the scores in order to specify the effect of the condition on the physiological and psychological data.
- *Analyse B:*
 - K means non-hierarchical clustering will be performed with K = 2. To categorise participants depending on their resting neurovegetative profile (low vagal tone / high vagal tone) and on their dynamical neurovegetative profile (low vagal flexibility / high vagal flexibility), two K means non-hierarchical clustering will be performed with K = 2. One with HF or RMSSD and one with Δ HF or Δ RMSSD.
 - Student's test for independent samples (dysfunctional neurovegetative profile / functional neurovegetative profile) will be performed on the psychological vulnerability (trait scores) collected.
- *Analyse C:*
 - An ANOVA to repeated measurement with an intra factor (measurement time: T2 / T3) and an inter factor (neurovegetative profile: dysfunctional profile / functional profile) on the physiological and psychological data collected only into the experimental group performing the BFB technique.
- *Correlational analysis:*

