 - Regressions or the Pearson correlations will be performed in order to measure the inter-signal correlation (ECG-EGG-EEG)
 - Regressions or the Pearson correlations will be performed in order to test our hypothesis about the HF/RMSSD related to the "low vagal tone" profile will be more correlated to Δ HF/RMSSD related to the "low vagal flexibility" profile than to Δ HF/RMSSD related to the "high vagal flexibility" profile. As the same as HF/RMSSD related to the "high vagal tone" profile will be more correlated to Δ HF/RMSSD related to the "high vagal flexibility" profile than to Δ HF/RMSSD related to the "low vagal flexibility" profile

Additional analyses

- We will control the age effect and the gender effect.
- Some additional statistical analyses will be exploratory: stability of the resting and the dynamical neurovegetative endophenotypes before the control period (T1) and at the end of the control period (T2).
- Correlation between the LF 0.1Hz and the clinical outcomes.
- To confirm the physiological effects of the BFB (BFB vs pseudo-BFB) on the flexibility of the electrophysiological coupling concerning the brain-visceral axis.

Sample

Power analysis (G * Power; Faul et al., 2007) was performed to determine a priori the sample size needed for this study. The power analysis, for an ANOVA (repeated measures, within-between factors), was performed for an effect size (η_p^2) of .12 with a power of .95 on the main judgment criterion (HRV – vagal tone HF) and reported a necessary sample of at least 22 participants (Kudo et al., 2014; Paul & Garg, 2012; Wells et al., 2012). We decided to include at least 25 IBS patients SII (20 test & 5 control) and 22 PNES patients (20 test & 5 control) in accordance with the possible inclusion rate and the duration of the study.

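### Analyses B and C: two separate K = 2 clusterings produce four vagal profiles, but only two are defined and tested, and the index, change score and direction that set membership are left open

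*Combined protocol and SAP*

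**What the plan says.** All places are in the SAP part of the combined document.

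- **Independent variables, Analyses B and C.** A cluster analysis of T1 data on HF or RMSSD divides participants into two groups: "A dysfunctional neurovegetative profile (low vagal tone + low vagal flexibility) group" and "A functional neurovegetative profile (high vagal tone + high vagal flexibility) group". Analysis B takes in everyone. Analysis C is limited to the biofeedback group.
- **Statistical analyses, Analyse B.** The opening sentence announces one K-means clustering with K = 2 and names no input variables. The next sentence separates a resting profile (tone) from a dynamical profile (flexibility) and says that "two K means non-hierarchical clustering will be performed with K = 2. One with HF or RMSSD and one with" the corresponding delta. The test that follows is Student's test for "independent samples (dysfunctional neurovegetative profile / functional neurovegetative profile) will be performed on the psychological vulnerability (trait scores) collected".
- **Statistical analyses, Analyse C.** A repeated-measures ANOVA over T2 and T3 with "an inter factor (neurovegetative profile: dysfunctional profile / functional profile").
- **Dependent variables, physiological adaptation.** Three HRV change scores are defined: task minus rest ("Physiological reactivity during the task compared to the resting period"), recovery minus task, and recovery minus rest ("Physiological recovery following the task compared to the resting period").

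The session used for clustering (T1) and the subtraction order of each change score are fixed. The plan does not state how the two sets of labels are combined, which change score is clustered, or which direction means high flexibility.

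**The concern.** A participant can have low tone with high flexibility, or high tone with low flexibility. Neither combination has a name, a level in the t-test or a level in the ANOVA, so an analyst following the text has nowhere to put these people. Leaving them out contradicts the statement that B includes everyone. Putting them in needs a rule that the plan does not contain.

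B is the plan's comparison of trait vulnerability by vagal profile. C is its test of whether the T1 profile modifies the response to biofeedback. For both, the text leaves room to settle who counts as dysfunctional or functional, and who is dropped, after the clusters are known. A low/low versus high/high contrast also cannot show whether tone or flexibility carries a difference.

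**Working it through.** **1. The plan's own figure.** The only sample-size figure is 22, in the Sample section. It reproduces for a time-by-group interaction with 2 groups and 3 times, assuming a within-person correlation of .5 and sphericity:

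- f² = .12/.88 = .136
- λ = .136 × 22 × 3/(1 − .5) = 18.0
- df = 2 and 40, power .964

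It concerns Analysis A's design and says nothing about profile groups in B or C.

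**2. The cells.** Two clusterings with K = 2 give 2 × 2 = 4 combinations:

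| | Low flexibility | High flexibility |
|---|---|---|
| **Low tone** | dysfunctional | not defined |
| **High tone** | not defined | functional |

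**3. The open choices.** If the same index is used in both clusterings and direction is either a rise or a fall, there are 2 indices × 3 change scores × 2 directions = 12 possible definitions. Reversing the direction swaps every flexibility label, so each concordant participant becomes discordant and each discordant one becomes concordant.

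**4. How many could be discordant.** The documents give no correlations or variances, so this step rests on assumptions: HF is log-normal and clustered as ln HF, SDs are equal at rest and in the task, the rest-task correlation ρ is .5, .7 or .9, the change score is task versus rest, and a larger fall means higher flexibility. The sample is 50 for B (40 + 10 in the allocation text) and 40 for C, with clusters formed within the 40.

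The correlation of resting level with the fall is r = √((1 − ρ)/2). With normal variables split at their centres, the expected discordant share is arccos(r)/π. Simulation with exact one-dimensional 2-means (6,000 replicates) allows for the sampling of the cut points.

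| ρ | r | Share | Formula, of 50 | Simulated, of 50 | Formula, of 40 | Simulated, of 40 |
|---|---|---|---|---|---|---|
| .5 | .500 | .333 | 16.7 | 16.9 | 13.3 | 13.6 |
| .7 | .387 | .373 | 18.7 | 18.9 | 14.9 | 15.1 |
| .9 | .224 | .428 | 21.4 | 21.5 | 17.1 | 17.2 |

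The smaller of the two concordant cells averages 11 to 14 in B and 9 to 11 in C.

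**5. Sensitivity of that count (of 50).**

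- Opposite direction, so that a larger task-minus-rest value means high flexibility: 28 to 33.
- Recovery minus task (rest-recovery correlation .85): 20 to 27. Recovery minus rest: about 29.
- Task/rest SD ratio .7: 11 to 13. Ratio 1.3: 20 to 29.
- Raw rather than log HF: about 2 to 4 at ratio .7, 7 to 13 at ratio 1.0, and 28 to 41 at ratio 1.3.
- Two true profiles, 2 to 3 within-profile SDs apart on both variables: 6 to 14.

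**6. Does the missing rule cost power?** For a linear effect with an assumed R² of .16 and N = 50:

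- two-cell t-test: .43 to .69
- all four labelled cells kept, 2-df test: .52 to .60
- one joint K = 2 clustering that places everyone, t-test: .43 to .68
- 2-df regression on the continuous measures: .74 to .76

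Placing the discordant participants recovers little. Most of the gap to the regression comes from dichotomising. The ranking also reverses under other truths. If the trait steps at the profile borders, the two-cell test has .72 to .74 against .56 to .58 for regression. With two true profiles it has .60 to .77 against .50 to .65.

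**The case against.** **One clustering may have been meant.** Analyse B opens with a single K-means sentence, the definitions speak of one cluster analysis that yields two groups, and B is said to include everyone. On this reading one exhaustive clustering makes the profiles, the two marginal clusterings serve the correlational and stability analyses, and nobody lacks a group. This stands as a possibility, so a reader should not infer that discordant participants are certainly excluded. It is the less natural reading, because the detailed sentence assigns one clustering to each variable and no inputs are given for a joint one. It does not remove the conflict, and index, change score and direction stay open. Under the base assumptions, a joint clustering would also give 17 to 22 of 50 a profile name that contradicts one of their two separate labels.

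**The correlational analysis is not proof.** It compares low tone with both low and high flexibility, and a reader might infer that the plan relies on a discordant subgroup. The wording is loose and could simply predict that low tone goes with low flexibility and high with high. It fits four cells but does not establish them.

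**Power is not the argument.** A reader might infer that the missing rule is what weakens B and C, or that continuous regression should replace the profiles. The comparison above supports neither.

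**Reach is limited.** The plan does not say that groups will be chosen after the clusters are seen. It only leaves that open.

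**Conclusion.** The concern holds as an internal conflict: two clusterings with four possible outcomes feed analyses with two levels, and one of those analyses is said to include everyone. Three unfixed choices decide membership. This needs correcting in the SAP because it determines who is analysed in B and C.

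The size is not fixed by the documents. About 17 to 22 of 50 and 14 to 17 of 40 is an illustration that depends on log-normal HF, equal SDs, a rest-task correlation of .5 to .9 and flexibility meaning a fall. Across the other settings tried, the count runs from about 2 to 41 of 50. The conflict does not depend on any of these figures.

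A reader might infer that the trial's main result is at risk. It is not: Analysis A and the main HF criterion do not use the profiles.

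**What to change.** Before the T1 clusters are seen, amend the SAP as follows.

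- **Reconcile** the group definitions for Analyses B and C with the clustering text in Analyse B.
- **Index:** fix HF, the stated main criterion, and the scale on which it is clustered. Use RMSSD as a sensitivity analysis.
- **Change score:** name one of the three, and the direction that means high flexibility.
- **Use all participants:** enter the tone label and the flexibility label as two factors in B, and each by time in C. Make low/low versus high/high a pre-specified contrast. Count and report the discordant cells.
- **Supporting analysis:** pre-specify a regression on continuous T1 resting ln HF and the named reactivity measure. It need not be the main analysis, since which form is more powerful depends on whether the relation is linear or made of distinct profiles.

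The cost is SAP wording and a little more analysis, with no new data. The downside is small discordant cells: under the base assumptions about 8 to 11 each in B (half of 16.9 to 21.5) and 7 to 9 each in C (half of 13.6 to 17.2). If the change score is taken from rest, tone and flexibility share the resting value, so their separate effects will be estimated less precisely.

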The emotional reactivity computerized task was developed specifically for our protocol with OpenSesame® software. The task looks like a type of stroop task. Instructions are to identify as soon as possible the ink color of the word on the screen matches the meaning of the word, in doing as less as possible mistake. We ask to the participants to press a specific button on the keyboard in the case of the ink color of the word matches the meaning of the word and to press on another button on the keyboard if they don't. We developed the task in 3 similarly but not identical versions with the aim of randomly testing the 3 versions on each participant. Each version lasts 12 minutes and has some particularities such as the colors of the words. We generated 3 versions of the task in the aim to limit the classical habituation effect in participants. Each version is made of 6 blocs in 20 trials that is aiming at progressively increasing the stress level because of an increase of the mental load. Bloc 1¹ and bloc 2 are associated with a low stress, bloc 4 and bloc 5 are associated with a moderate stress and bloc 5 and bloc 6 are associated with a high stress. The increase of the mental load is permitted by slowly decreasing the word presentation time, by putting feed-back, instruction switches, time constraints and lastly, by the necessity to do a dual task.

STAI Y-A / PANAS / CES-D / PSS / CFS / SWLS / ICQ-18	ECG/EGG/EEG/ GSR/PPG/Emwave/ respiratory belt positioning	Resting period (30 minutes, seated, eyes closed)	Reactivity period (during the task, seated)	VAS	Recovery period (30 minutes, seated, eyes closed)
--	---	--	---	-----	---

3h30

The period (24 days) between the first session and the second session (T1-T2) will be considered as the control period. The larger BFB effects than the unspecific effects related to the spontaneous physiological and emotional variations will be verified through the control period. We will measure the parameters of interest before (T1) and at the end of the control period (T2). During the period, the participants will have to answer to online questionnaires (SSQ6, MAIA-2, STAI Y-B, Brief-Cope, BFI-N, CTQ) aiming to examine the psychological profile (social support, interceptive sensitivity, trait anxiety, style of coping, early life events).

The second session (T2), T1 + 24 days, will be similar of the first session. We will use the same questionnaires and will record the same electrophysiological parameters. At the end of the

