[figure not shown]
¹ The bloc 1 will not be included in the final statistical analysis because is considered as a training bloc. This choice in accordance to the potential biases related to the increase of the sympathetic activity at the beginning of the task caused by a simple moving to action following the resting period.

second session, a short training session of the biofeedback [BFB] technique will be done and the software using for the biofeedback training will be supplied to each participant included in the experimental group to allowed to us to practice BFB by their self at home. The installation of the program and the explanations needed for using it, will be done during the second session (T2). The BFB software (Emwave Pro®) includes a photoplethysmography sensor that can be positioned on the earlobe. The participants will have to practice the biofeedback technique the next 24 days (3X5 min/day).

The period (24 days) between the second session and the third session (T2-T3) will be considered as the intervention period. At the end of the second session (T2), the participants will be separated into two inter-subject groups: an experimental group performing BFB technique (3X5 min per day) in the intervention period (T2-T3) and a control group not performing a specific exercise in the intervention period (T2-T3). The first 40 participants (20 IBS / 20 PNES) will be included into the experimental group (BFB training) whereas the last 10 participants (5 IBS / 5 PNES) will be included into the control group (no training). The participants won't be informed of the condition to which they belong. We will measure the parameters of interest before (T2) and at the end of the intervention period (T3). During the intervention period, all the participants will have to answer to online questionnaires (BVAQ-B, LES, DHS) aiming to examine the psychological profile (alexithymia, traumatic events).

The third session (T3), T2 + 24 days, will be similar of the two previous sessions. We will use the same questionnaires and will record the same electrophysiological parameters. Finally, a debriefing will be done at the end of the session for each participant. The session will be considered as the end of the study visit.

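### Analysis C compares vagal profiles only among biofeedback users at T2 and T3, so it cannot by itself show that one profile benefits more from biofeedback

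*Combined protocol and SAP*

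**What the plan says.** The SAP describes Analysis C twice, and the two descriptions agree. Under Independent variables the population is given as "We will include only the experimental group performing the BFB technique" and the within-subject factor as "Measurement time (T2 / T3) intra-subject". Under Statistical analyses the model has the same two factors, time and neurovegetative profile, on data "collected only into the experimental group performing the BFB technique". Profile is fixed earlier, by K-means clustering of HF or RMSSD (and of their task-related deltas) at T1.

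The Study protocol section provides two references for change that is not due to BFB. One is the T1-T2 interval: "The larger BFB effects than the unspecific effects related to the spontaneous physiological and emotional variations will be verified through the control period". The other is an untrained group. For allocation, "The first 40 participants (20 IBS / 20 PNES) will be included into the experimental group", and the last 10 (5 IBS, 5 PNES) form the control group. Analysis C uses neither reference.

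**The concern.** In a single trained arm, the Profile x Time interaction is the T2-T3 change in the dysfunctional profile minus that in the functional profile. It is the sum of three parts:

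- the difference between profiles in the BFB effect;
- the difference between profiles in change that would have happened anyway (natural course, habituation to a third stress session);
- any regression to the mean still running after T2, because the profiles were formed on T1 values.

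Two visits in one arm give one equation for these three unknowns. A significant interaction shows that the profiles changed differently while BFB was being practised. It does not show that BFB worked differently in them. At stake is a statement about which patients gain from BFB, which could guide later patient selection.

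**Working it through.** **1. The plan's own figure.** The Sample section gives 22 participants for partial eta squared .12 and power .95. Assumed, because not stated: 2 groups, 3 times, correlation 0.5, no sphericity correction. Then f² = .12/.88 = 0.1364 and lambda = f² x N x m/(1 - rho) = 0.1364 x 22 x 3/0.5 = 18.0 on 2 and 40 df, with power 0.964. The smallest N is 21, or 22 with equal groups, so the figure reproduces. It has the shape of Analysis A. The 2 x 2 shape of Analysis C needs 26 on the same assumptions, and 40 BFB users exceed that. Sample size is therefore not the problem in Analysis C; the missing comparator is.

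**2. Which analysis contains what.**

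| Analysis | Profile | Controls | Time |
|---|---|---|---|
| A | no | yes | T1/T2/T3 |
| B | yes | yes | none (trait scores) |
| C | yes | no | T2/T3 |

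The exploratory check of profile stability from T1 to T2 is not linked to Analysis C. No planned analysis has profile, group and time together.

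**3. Effect of profile-specific drift.** Assumptions: no BFB effect, 20 patients per profile, two-sided alpha 0.05. In units of the SD of change, SE = sqrt(1/20 + 1/20) = 0.316 on 38 df. In outcome SD at test-retest 0.7, the SD of change is sqrt(2 x 0.3) = 0.775 and SE = 0.245. Rejection rates come from the noncentral t with noncentrality drift/SE.

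| Drift difference | Rate, unit = SD of change | Rate, unit = outcome SD, test-retest 0.7 |
|---|---|---|
| 0.1 | 0.1/0.316 = 0.32: 6% | 0.1/0.245 = 0.41: 7% |
| 0.3 | 0.95: 15% | 1.22: 22% |
| 0.4 | 1.26: 23% | 1.63: 36% |

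**4. Regression to the mean, with no drift and no BFB effect.** Simulation used a simplified one-variable K-means (K = 2) on T1 HF in 40 BFB users.

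- Equal correlations between all visits: the whole effect falls between T1 and T2. The profile gap in T1-T2 change is about 0.82 SD at correlation 0.5 and 0.49 SD at 0.7. The gap in T2-T3 change is about 0, and Analysis C rejects in about 5%.
- AR(1) correlations: the gap between clusters at T1 is about 0.82/(1 - 0.5) = 1.64 SD. It shrinks to rho x 1.64 at T2 and rho² x 1.64 at T3, so the T2-T3 gap is rho(1 - rho) x 1.64. That is 0.41 SD at rho 0.5 and 0.34 SD at 0.7. Analysis C then rejects for HF/RMSSD in about 21% to 29%.

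**5. Adding the controls.** With 5 controls per profile (assumed), the Profile x Group x Time contrast has SE = sqrt(1/20 + 1/20 + 1/5 + 1/5) = 0.707 SD of change. That is 0.707/0.316 = 2.24 times the SE of Analysis C. In simulation with comparable controls it rejected in about 4% to 6% under every drift and correlation pattern tried. Power for a true 0.5 outcome-SD difference is about 11% (test-retest 0.5) to 15% (0.7).

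**6. Adding T1 instead.** The contrast (T3 - T2) - (T2 - T1) has variance 6(1 - rho) against 2(1 - rho) for T3 - T2, so its SE is sqrt(3) = 1.73 times larger. For outcomes correlated 0.7 to 0.9 with the clustering variable it carries the regression to the mean of step 4. With equal between-visit correlations and no true effect it rejects in about 13% to 27%, where Analysis C stays near 5%. It also removes only drift that is equal in both intervals.

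**The case against.** The strongest reply is that the SAP nowhere says Analysis C tests moderation. It lists factors and a test, with no hypothesis or planned interpretation. This is right, so the point has to be conditional on how the result is used.

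A reader might also infer that Analysis C breaks the commitment to verify BFB effects against spontaneous variation through the control period. The documents do not support that reading. The sentence does not promise the check in every analysis, and Analysis A, with T1, T2, T3 and the controls, addresses it for the study as a whole. It does so without profile, so the gap by profile remains.

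Two features mitigate the problem in part. Three versions of the task are meant to limit habituation, and the stability of the profiles from T1 to T2 is to be explored. Forming the profiles at T1 rather than T2 also protects the T2-T3 comparison against regression to the mean, fully so if between-visit correlations are equal. None of these removes a spontaneous change that differs between profiles.

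Finally, the control group is small and was included last, so a three-way estimate will be imprecise and confounded with calendar time. This stands too. It is a reason to call the estimate exploratory, but it does not make the one-arm comparison informative about moderation.

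**Conclusion.** The point holds in conditional form. Analysis C can describe change during BFB by profile. It cannot attribute a difference in that change to BFB, and no other planned analysis fills the gap.

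The size of the error is not known. The rates of about 6% to 23% (SD of change) or 7% to 36% (outcome SD, test-retest 0.7) rest on an assumed drift of 0.1 to 0.4 SD and an assumed 20/20 split. At the low end they hardly differ from 5%. The 21% to 29% for HF/RMSSD without drift needs AR(1) correlations of 0.5 to 0.7. The profiles combine two separate clusterings (tone and flexibility), so patients who are low on one and high on the other may fit neither group, and the real split may be smaller or uneven.

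A reader might infer that Analysis C will certainly produce a false claim of moderation, or that it is too small. The documents support neither: the bias is a risk that depends on unknown drift and correlations, and the plan's own power assumptions are met by 40 BFB users.

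**What to change.** 1. State in the SAP that the T2/T3 test in BFB users describes change during BFB by profile, and that it will not be reported as moderation of the BFB effect.
2. For every outcome measured at both T2 and T3, add an exploratory Profile x Group x Time (T2/T3) estimate with its confidence interval, including the 10 controls. Report the controls' change by profile beside it.
3. If a (T3 - T2) minus (T2 - T1) contrast is also reported, limit it to outcomes neither derived from nor strongly correlated with the clustering variables. That excludes HF, RMSSD, total power (which contains the HF band), LF/HF (which has HF as denominator), SDNN and the HRV deltas. State that the contrast assumes equal non-specific change in the two intervals.

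The cost is in analysis and wording only, since the data are already part of the plan. The three-way estimate has an SE about 2.24 times larger if the controls split 5/5, and more if the split is uneven. The difference detectable with 80% power rises from 0.91 to 2.03 SD at correlation 0.5. Because the controls are the last 10 included, calendar time is confounded with group, and the report should say so. A non-significant three-way result must not be read as evidence that the profiles respond equally.
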